6.20 Assessment of outcomes

The investigator will assess the outcome of all AEs (including SAEs) recorded during the study as:

- Recovered/resolved.
- Recovering/resolving.
- Not recovered/not resolved.
- Recovered with sequelae/resolved with sequelae.
- Fatal (SAEs only).

6.21 Safety (ANALYSIS)

- Safety and reactogenicity of the investigational vaccine for each vaccination schedule:
 - Occurrence of solicited local and general AEs within seven days (day of vaccination and six subsequent days) after each vaccination.
 - Occurrence of unsolicited AEs from the date of the first vaccination to 29 days after the last vaccination, according to the Medical Dictionary for Regulatory Activities (MedDRA) classification.
 - Occurrence of SAEs (all, fatal, related to investigational vaccine) within 30 days (day of vaccination and 29 subsequent days) after each vaccination, according to the MedDRA classification.
 - Occurrence of SAEs (all, fatal, related to investigational vaccine) during the whole study period according to the MedDRA classification.
 - Occurrence of AEs and SAEs leading to withdrawal from further vaccination from Dose 1 (Day 0) up to study conclusion (Day 180), according to the MedDRA classification, for each vaccinated subjects.
 - Occurrence of pIMDs from Dose 1 (Day 0) up to study conclusion (Day 180), according to the MedDRA classification, for each vaccinated subjects.
 - Occurrence of meningitis from Dose 1 (Day 0) up to study conclusion (Day 180), according to the MedDRA classification, for each vaccinated subjects.

6.22 Analysis of safety

The percentage of subjects with at least one local AEs with at least one general AE (solicited and unsolicited) and with any AE during the 7-day or total follow-up period up to 29 days after the last vaccine dose and overall will be tabulated with exact 95% CI. The percentage of doses followed by at least one local AE (solicited and unsolicited), by at least one general AE (solicited and unsolicited) and by any AE during the 7-day or the total follow up period up to 29days after the last vaccine will be tabulated with exact 95% CI. The same computations will be done for Grade 3 AEs, for any AEs considered related to vaccination and for any Grade 3 AEs considered related to vaccination.

The percentage of subjects reporting each individual solicited local AE (any grade and Grade 3) and solicited general AE (any grade, Grade 3, any related, Grade 3 related, resulting in medically attended visit) during the 7-day follow-up period (Day 0-6) after each vaccine dose and overall will be tabulated for each group. Similarly, the percentage of doses followed by each individual solicited local and general AE will be tabulated, overall vaccination course, with exact 95% CI.

For fever, the number and percentage of subjects reporting fever by half degree (°C) cumulative increments during the first seven days (Day 0-6) after each vaccine dose and overall will be tabulated. Similar tabulations will be performed for any fever with a causal relationship to vaccination and Grade 3 (> 39.5°C) causally related fever.

The percentage of subjects reporting unsolicited AEs from the date of the first vaccine dose up to 29 days after the last vaccine dose and after the sporozoite challenge will be tabulated by group and by MedDRA preferred term with exact 95% CI. Similar tabulation will be done for Grade 3 unsolicited AEs, for any causally related unsolicited AEs and for Grade 3 causally related unsolicited AEs.

The percentage of subjects reporting SAEs and pregnancies will be described in detail.

The percentage of vaccinated subjects reporting AEs of specific interest (meningitis and pIMDs) will be described in detail.

Biochemistry (ALT, AST and creatinine) and haematological (haemoglobin, WBC and platelets) laboratory values will be presented according to toxicity grading scales and tabulated by group.

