1 SYNOPSIS

Study Title	Safety and immunogenicity evaluation of the malaria vaccine, RTS,S/AS01, in healthy Thai adults
Study Design	Randomized, open label, single centre, Phase 2 study
Study Participants	
190 healthy non-pregnant Thai adults, aged 18-55 years, inclusive, will be recruited.
Study arms	
See Table 3 for dosing table
 
1. RTS,S/AS01B Fractional dose group (Group 1, n=20) will receive RTS,S/AS01B standard dose at Month 0 and Month 1 + RTS,S/AS01B fractional dose (1/5th dose) at Month 2.2. Double RTS,S/AS01E Fractional dose group (Group 2, n=20) will receive a double dose of RTS,S/AS01E standard dose at Month 0 and Month 1 + a double dose of RTS,S/AS01E fractional dose (1/5th dose) at Month 2.3. RTS,S/AS01E Standard dose group (Group 3, n=30) will receive RTS,S/AS01E standard dose at Month 0, Month 1 and Month 2.4. RTS,S/AS01E + DHA-PIP+PQ Standard dose group (Group 4, n=30) will receive RTS,S/AS01E standard dose + DHA-PIP+PQ at Month 0, Month 1 and Month 25. RTS,S/AS01E Fractional dose group (Group 5, n=30) will receive RTS,S/AS01E standard dose at Month 0 and Month 1 + RTS,S/AS01E fractional dose (1/5th dose) at Month 2.6. RTS,S/AS01E + DHA-PIP+PQ Fractional dose group (Group 6, n=30) will receive RTS,S/AS01E standard dose + DHA-PIP+PQ at Month 0 and Month 1 + RTS,S/AS01E fractional dose (1/5th dose) + DHA-PIP+PQ at Month 2.7. RTS,S/AS01E + DHA-PIP+PQ Fractional two-dose group (Group 7, n=30) will receive RTS,S/AS01E standard dose + DHA-PIP+PQ at Month 0 + RTS,S/AS01E fractional dose (1/5th dose) + DHA-PIP+PQ at Month 2.

	
Standard dose RTS,S/AS01B: 50µg RTS,S + standard dose AS01B (0.5ml containing 50µg MPL + 50µg QS21)
 
Standard dose RTS,S/AS01E: 25µg RTS,S + standard dose AS01E (0.5ml containing 25µg MPL + 25µg QS21)
 
Fractional dose RTS,S/AS01B (1/5th dose): 10µg RTS,S + 1/5 standard dose AS01B (0.1ml containing 10µg MPL + 10µg QS21)
 
Fractional dose RTS,S/AS01E (1/5th dose): 2.5µg RTS,S + 1/5 standard dose AS01E (0.1ml containing 2.5µg MPL + 2.5µg QS21)
 
DHA-PIP: Dihydroartemisinin–piperaquine co-formulated, given on day of vaccination (day 0) and each of the subsequent two days (days 1 and 2 post-vaccination).
 
PQ: Primaquine, given on day of vaccination (day 0).

Number of vaccine vials needed	
 • 60 vials RTS,S/AS01B (adult formulation) • 540 vials RTS,S/AS01E (standard formulation)

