7 HOLDING RULES AND SAFETY MONITORING

7.1. No group holding rules will be pre-defined considering the evidence for a favourable safety profile of this candidate vaccine in Phase III infant evaluation.

7.2. Individual subject holding rules. Individual study participants who present at least one of the following stopping rules for individual subjects will be withdrawn from further vaccination:

- a) Local reactions: upon investigator discretion.
- b) Systemic solicited adverse events: The subject develops a Grade 3 systemic solicited adverse event beginning within 2 days after vaccination (day of vaccination and one subsequent day) and persisting at Grade 3 for >2 consecutive days.
- c) Unsolicited adverse events: The subject has any Grade 3 adverse event considered related to vaccination, persisting at Grade 3 for >2 consecutive days.

- d) The subject has a serious adverse event considered related to vaccination.
- e) The subject has an acute allergic reaction or anaphylactic shock following the administration of vaccine investigational product.
- f) Laboratory adverse events: The subject has any Grade 3 laboratory adverse event considered related to vaccination.

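### Section 6.22 puts exact binomial 95% CIs on pooled doses, ignoring that two or three doses come from the same person, so the stated 95% level is not assured

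*Protocol*

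**What the plan says.** Protocol section 6.22 asks for dose-level percentages in two places. The first paragraph covers summaries of any AE: "The percentage of doses followed by at least one local AE (solicited and unsolicited), by at least one general AE", and any AE overall, each with an exact 95% CI. It then extends this: "The same computations will be done for Grade 3 AEs, for any AEs considered related to vaccination", and for Grade 3 related AEs. The second paragraph covers individual solicited symptoms over the whole course: "the percentage of doses followed by each individual solicited local and general AE will be tabulated, overall vaccination course, with exact 95% CI".

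Subject-level percentages are also planned. The first paragraph gives them an exact 95% CI for the at-least-one-AE summaries. For individual symptoms the text is "The percentage of subjects reporting each individual solicited local AE (any grade and Grade 3") and the corresponding general AEs, to be tabulated by group after each dose and overall. No interval is stated in that sentence.

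The Synopsis and Table 3 (section 8.2) fix the doses per person: three in Groups 1 to 6 and two in Group 7. Groups 1 and 2 have 20 participants each, the others 30. The last dose is fractional in Groups 1, 2, 5, 6 and 7. Only Groups 3 and 4 receive three equal doses. Section 7.2 adds that "Individual study participants who present at least one of the following stopping rules for individual subjects will be withdrawn from further vaccination", so the number of doses per person can depend on earlier reactions.

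**The concern.** In these tables the unit of analysis is the dose. A person who reports pain, headache or fatigue after one injection is ordinarily more likely to report it after the next. If so, 90 doses from 30 people carry less information than 90 independent observations, and a binomial interval on 90 is too short. The degree also differs by arm, because Group 7 has two doses per person and the other groups three.

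What is at stake is the precision claimed for reactogenicity. Section 3 lists safety comparisons between regimens among the objectives (Group 1 against 2, 1 against 5, 2 against 5), and 6.22 names no between-group safety test. Readers may therefore set the arms side by side through these intervals. As 6.22 is worded, the only interval stated for each individual solicited symptom is the dose-level one.

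**Working it through.** **Inputs.** From the protocol: 30 × 3 = 90 doses in each of Groups 3 to 6, 20 × 3 = 60 in Groups 1 and 2, and 30 × 2 = 60 in Group 7, if all doses are given. Assumed, because the protocol gives neither: ICC from 0 to 0.5 and reaction rate per dose from 10% to 80%. The protocol states no dose-level interval or design effect, so there is no figure of its own to reproduce.

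**Standard error.** Design effect DE = 1 + (m − 1) × ICC, where m is doses per person. The correct SE is √DE times the pooled SE. The pooled SE is therefore too small by 1 − 1/√DE.

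| m = 3, ICC | DE | correct SE larger by | pooled SE too small by |
|---|---|---|---|
| 0.2 | 1.4 | 18% | 15% |
| 0.3 | 1.6 | 26% | 21% |
| 0.5 | 2.0 | 41% | 29% |

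For Group 7 (m = 2) the DE is 1.2 / 1.3 / 1.5.

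**Interval for 45 of 90 doses (50%).** Clopper-Pearson on the pooled doses gives 39.3 to 60.7%. The same method on the effective number of doses (90/DE) gives:
- ICC 0.2, effective n 64.3: 37.3 to 62.7% (1.19 times as wide)
- ICC 0.3, effective n 56.2: 36.4 to 63.6% (1.27 times)
- ICC 0.5, effective n 45: 34.7 to 65.3% (1.42 times)

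**Coverage of the nominal 95% pooled interval.** Simulated with beta-binomial clusters, so every dose of a person has the same rate.

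| Setting | ICC 0 | 0.1 | 0.2 | 0.3 | 0.5 |
|---|---|---|---|---|---|
| 30 × 3, rate 50% | 95.6% | 93.4% | 90.8% | 88.6% | 84.3% |
| 30 × 3, rate 10% | 96.5% | 95.0% | 92.8% | 90.7% | 86.6% |
| 20 × 3, rate 50% | 97.3% | 95.5% | 93.7% | 91.8% | 88.1% |
| 30 × 2, rate 50% | 97.4% | 96.5% | 95.5% | 94.6% | 92.7% |

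Exact intervals are conservative when doses are independent. That is why some correlation can be absorbed before coverage falls clearly below 95%.

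**Unequal rates across doses.** Equal rates fit Groups 3 and 4 by design. For arms with a fractional last dose, a logit-normal random-intercept model with a lower rate at dose 3 gives the coverage below.

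| Setting, rates at doses 1 / 2 / 3 | SD 0 | SD 1 | SD 2 |
|---|---|---|---|
| 30 × 3, 80/80/40% | 98.1% | 96.3% | 93.5% |
| 30 × 3, 60/60/40% | 96.1% | 92.2% | 87.7% |
| 20 × 3, 80/80/40% | 97.5% | 95.3% | 92.3% |
| 20 × 3, 60/60/20% | 98.4% | 96.5% | 93.5% |

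With 90/90/30% and 30 people, coverage stays above 97% throughout. With the mild drop 80/80/65% and SD 2 it is about 89%. A large drop can therefore cancel or outweigh the clustering, and a small one does not.

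**The case against.** The strongest reply is that neither the correlation nor the reaction rates are in the protocol, and that an equal-rate model does not fit five of the seven arms. All three named safety comparisons (Groups 1, 2 and 5) lie among those five, where a fall in reactions at the fractional dose can bring coverage back to nominal or above. This stands. A reader might infer from the equal-rate figures that every dose-level interval under-covers, or that arms will look more different than they are. The documents support neither reading. The direction in the fractional-dose arms depends on unknown rates, and no comparison of intervals is prescribed.

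A second reply is that nothing rests on these intervals. Section 6.22 only tabulates. The sample size (8.2), the individual holding rules (7.2) and the primary SAE outcome (4.2) do not use a dose-level CI. This also stands, and it limits the consequence.

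A third reply is that the subject-level percentages are free of clustering and already planned. This stands only in part. The at-least-one-AE summaries have exact CIs, but the sentence on individual solicited symptoms states none, so as worded it offers no sound interval in place of the dose-level one.

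None of these replies makes a binomial interval on repeated doses correct. They bear on how far wrong it is and how much that matters.

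**Conclusion.** The point holds in a limited form. Section 6.22 fixes an interval that treats repeated doses from one person as independent, so its 95% level is not assured.

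For three equal-rate doses in 30 people (Groups 3 and 4) at a 50% rate, coverage is about 91 / 89 / 84% at an assumed ICC of 0.2 / 0.3 / 0.5. It is about 93 to 95% or better at an ICC of 0.1 or below. In Group 7 it remains near nominal up to about 0.3. In the arms with a fractional last dose it may be low, nominal or conservative, depending on how far reactions fall at that dose.

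It would go too far to say that 95% coverage is definitely missed in every arm, or that a safety conclusion is put in doubt. What is affected is the stated precision of descriptive dose-level reactogenicity tables. The correction is cheap and worth making.

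**What to change.** In section 6.22, state that the 95% CI for any percentage of doses is computed with the participant as the cluster, by participant-level bootstrap or robust variance and allowing for dose number. Alternatively, show pooled dose percentages without a CI. The change should cover both dose-level sentences and the Grade 3 and related versions.

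Under either option, attach exact 95% CIs explicitly to the subject-level percentages for each solicited AE, after each dose and overall. Otherwise dropping the dose-level interval would leave individual symptoms with no stated interval.

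The cost is a sentence or two in 6.22, a changed table program and, in most settings, somewhat wider dose-level intervals. No further data, visits or participants are needed.

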6.6 *Solicited local (injection-site) adverse events*

The following local (injection-site) AEs will be solicited:

All age groups
Pain at injection site Redness at injection site Swelling at injection site

6.7 *Solicited general adverse events*

The following general AEs will be solicited:

Adult
Fatigue Fever Gastrointestinal symptoms † Headache

† Gastrointestinal symptoms include nausea, vomiting, diarrhoea and/or abdominal pain.

Note: Temperature will be recorded in the evening. Should additional temperature measurements be performed at other times of day, the highest temperature will be recorded in the CRF.

6.8 *Clinical laboratory parameters and other abnormal assessments qualifying as adverse events or serious adverse events*

In absence of diagnosis, abnormal laboratory findings (e.g. clinical chemistry, haematology, urinalysis) or other abnormal assessments that are judged by the investigator to be clinically significant will be recorded as AE or SAE if they meet the definition of an AE or SAE. Clinically significant abnormal laboratory findings or other abnormal assessments that are present at baseline and significantly worsen following the start of the study will also be reported as AEs or SAEs.

The investigator will exercise his or her medical and scientific judgment in deciding whether an abnormal laboratory finding or other abnormal assessment is clinically significant.

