6.18 Assessment of intensity

The intensity of the following solicited AEs will be assessed as described:

Intensity scales for solicited symptoms in adults

Adults		
Adverse Event	Intensity grade	Parameter
Pain at injection site	0	None
	1	Mild: Any pain neither interfering with nor preventing normal every day activities.
	2	Moderate: Painful when limb is moved and interferes with every day activities.
	3	Severe: Significant pain at rest. Prevents normal every day activities.
Redness at injection site		Record greatest surface diameter in mm
Swelling at injection site		Record greatest surface diameter in mm
Fever*		Record temperature in °C/°F
Headache	0	Normal
	1	Mild: Headache that is easily tolerated
	2	Moderate: Headache that interferes with normal activity
	3	Severe: Headache that prevents normal activity
Fatigue	0	Normal
	1	Mild: Fatigue that is easily tolerated
	2	Moderate: Fatigue that interferes with normal activity
	3	Severe: Fatigue that prevents normal activity
Gastrointestinal symptoms (nausea, vomiting, diarrhoea and/or abdominal pain)	0	Normal
	1	Mild: Gastrointestinal symptoms that are easily tolerated
	2	Moderate: Gastrointestinal symptoms that interfere with normal activity
	3	Severe: Gastrointestinal symptoms that prevent normal activity

*Fever is defined as temperature $\geq 37.5^{\circ}\text{C}$ / 99.5°F for oral, axillary or tympanic route, or $\geq 38.0^{\circ}\text{C}$ / 100.4°F for rectal route. The preferred route for recording temperature in this study will be oral.

The maximum intensity of local injection site redness and swelling will be scored as follows:

0	:	0 mm
1	:	> 0 to \leq 50 mm
2	:	> 50 mm to \leq 100 mm
3	:	> 100 mm

The maximum intensity of fever will be scored as follows:

0	:	< 37.5°C (< 99.5°F)
1	:	$\geq 37.5^{\circ}\text{C}$ ($\geq 99.5^{\circ}\text{F}$) to $\leq 38.0^{\circ}\text{C}$ (100.4°F)
2	:	> 38.0°C (> 100.4°F) to $\leq 39.0^{\circ}\text{C}$ (102.1°F)
3	:	> 39.0°C (102.1°F)

The investigator will assess the maximum intensity that occurred over the duration of the event for all unsolicited AEs (including SAEs) recorded during the study. The assessment will be based on the investigator's clinical judgment.

The intensity should be assigned to one of the following categories:

- 1 (mild) = An AE which is easily tolerated by the subject, causing minimal discomfort and not interfering with everyday activities.

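### Section 6.22 labels related fever as Grade 3 only above 39.5°C, while the protocol's only fever scale (6.18) sets Grade 3 above 39.0°C, so two planned Grade 3 counts could differ

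*Protocol*

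**What the plan says.** Section 6.18 gives the grading rule for fever. It opens with "The maximum intensity of fever will be scored as follows" and runs from 0 to 3: below 37.5°C is 0, 37.5 to 38.0°C is 1, above 38.0 and up to 39.0°C is 2, and intensity 3 is "> 39.0°C (102.1°F"). The protocol has no other fever grading scale.

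Section 6.7 lists the solicited general adverse events for adults: "Fatigue Fever Gastrointestinal symptoms † Headache". Fever is therefore one of them.

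Section 6.22 then plans two outputs in which Grade 3 related fever appears:

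- a subject-level table of the individual solicited general events, by group, over Day 0-6 for every dose and for the course as a whole, whose categories include "Grade 3 related, resulting in medically attended visit";
- a fever-specific table by half-degree "cumulative increments during the first seven days (Day 0-6) after each vaccine dose and overall will be tabulated", repeated for all related fever and for "Grade 3 (> 39.5°C) causally related fever".

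**The concern.** The same label, Grade 3, carries two cut-offs that differ by half a degree. Section 6.18 has fever recorded as a temperature, not as a grade, so the grade is derived at analysis and the cut-off applied decides the count. The two 6.22 tables cover the same participants, the same days and the same causality restriction. A reader would expect their Grade 3 related-fever rows to agree, and as written they need not.

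What is at stake is modest but visible. In arms of 20 or 30, a single participant separates an arm with no Grade 3 related fever from an arm with some. Comparing the safety of the regimens is a stated objective (section 3). Two different counts for one arm in the same report would leave the reader unsure which is right.

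**Working it through.** This is mainly a comparison of text, with a little arithmetic to show scale.

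**The two cut-offs**

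| Place | Purpose | Grade 3 fever |
|---|---|---|
| 6.18 | Scoring of maximum fever intensity | above 39.0°C |
| 6.22, individual solicited general events | Grade 3 and Grade 3 related, Day 0-6 | no temperature given; 6.18 is the only scale to apply |
| 6.22, fever-specific table | Grade 3 causally related, Day 0-6 | above 39.5°C |
| 7.2(b), individual holding rule | Grade 3 systemic solicited event | no temperature given; 6.18 is the only scale to apply |

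**Is the 6.18 figure itself a slip?** Its Fahrenheit equivalent is a check. 39.0 × 9/5 + 32 = 102.2°F and 39.5 × 9/5 + 32 = 103.1°F. Section 6.18 prints 102.1°F, which matches 39.0°C to within 0.1°F and is a full degree Fahrenheit from 39.5°C. Grade 2 in the same scale ends at 39.0°C, so the scale is consistent with itself. The figure out of line is the one in 6.22.

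**Which participants are affected?** Let T be the maximum temperature of a related fever within Day 0-6.

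- T up to 39.0°C: not Grade 3 under either cut-off.
- T above 39.0 and up to 39.5°C: Grade 3 under 6.18, not Grade 3 under the 6.22 label.
- T above 39.5°C: Grade 3 under both.

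The fever-specific count can therefore never exceed the other. The difference is the number of participants whose T lies in the middle band.

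**Size.** The protocol gives no expected frequency of fever in this band, so the expected difference cannot be calculated. As an illustration, assume one participant in the band and no hotter related fever in that arm:

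- arm of 30 (Groups 3 to 7): 1/30 = 3.3% against 0/30 = 0%;
- arm of 20 (Groups 1 and 2): 1/20 = 5.0% against 0/20 = 0%.

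Section 6.22 uses exact 95% confidence intervals in other tables but does not state them for these two rows. If they were added, the Clopper-Pearson limits would be:

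| Arm size | 6.18 cut-off (1 event) | 6.22 cut-off (0 events) |
|---|---|---|
| 30 | 0.1% to 17.2% | 0% to 11.6% |
| 20 | 0.1% to 24.9% | 0% to 16.8% |

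For zero events the upper limit is 1 − 0.025^(1/n): 1 − 0.025^(1/30) = 11.6% and 1 − 0.025^(1/20) = 16.8%. For one event the lower limit is 1 − 0.975^(1/n), which is 0.1% for both sizes. The upper limit solves (1 − p)^n + n·p·(1 − p)^(n−1) = 0.025, giving 17.2% for n = 30 and 24.9% for n = 20.

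**Per-dose tables.** The fever-specific table is planned by subject only, so the per-dose tables of solicited events have no conflicting counterpart.

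**The case against.** The best case on the other side accepts the mismatch and disputes its weight.

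- **No important result depends on it.** The primary safety outcomes are serious adverse events (4.2), 6.22 plans no between-group test on fever, and holding rule 7.2(b) names no temperature. This stands.
- **The data are shown anyway.** Half-degree cumulative tabulation is planned for all fever and, on the natural reading, for related fever too, so counts around both cut-offs would be visible. This stands and limits the harm. It does not tell a reader which row is the correct Grade 3 count.
- **Two conflicting counts are an inference.** Section 6.22 does not say which scale the individual solicited-event table uses. An analyst could apply 39.0°C throughout, or 39.5°C to both fever rows. That is fair, which is why the claim is only that the counts could differ. But the first choice departs from 6.22 and the second from 6.18, so no programming choice satisfies both sections.
- **It is probably leftover text.** Section 6.22 also mentions events after a sporozoite challenge, which this trial's schedule does not include. Carried-over wording is a plausible origin, though not proven. It is a reason to correct the figure, not to leave it.
- **The illustration rests on one hypothetical event, and the intervals are not planned for these rows.** Both are true, and both are stated as conditions above.

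**Conclusion.** The concern holds. Section 6.22 states a Grade 3 fever threshold that contradicts the protocol's only fever scale, and no text reconciles them. The effect is confined to descriptive reactogenicity tables. It appears only if at least one related fever peaks above 39.0 and up to 39.5°C, and the fever-specific count can then only be the lower one. One such participant, with no hotter related fever, is worth 3.3 percentage points in an arm of 30 or 5.0 in an arm of 20. The conclusion assumes that the individual solicited-event table is graded by 6.18, the only scale available. It should be corrected because the error is certain and the correction nearly free, not because it threatens a main result.

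**What to change.** In 6.22, change 39.5°C to 39.0°C in the sentence on Grade 3 causally related fever, or delete the parenthesis and refer to the scale in 6.18. Leave 6.18 and 7.2 as they are. If fever above 39.5°C is of interest in its own right, the planned half-degree tabulation can show it without a Grade 3 label. The cost is one figure in one sentence. Temperatures are already recorded, so diary cards, the CRF and visits do not change.
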